Chronic Pain Acceptance Questionnaire (CPAQ8)⁷⁶

Canadian Occupational Performance Measure (COPM)⁸¹

Roland-Morris Disability Questionnaire⁸⁰

Opioid utilization screener*

- Current opioid regimen
- Duration of pain and of opioid treatment
- Morphine equivalent dose
- Pain relief from opioids**

*Data on utilization and dosage are electronically extracted by PASTOR from the CHCS Electronic Medical Database.

**Patient self-reports pain relief if applicable.

Based on six months of experience with use of PASTOR at the Madigan Interdisciplinary Pain Management Center, the time required to complete this study's PASTOR measures is expected to be

approximately 20 minutes at baseline and 15 minutes at each follow-up time point. Because the PASTOR platform is a secure, web-based system, participants will have the option of completing PASTOR from the convenience of their homes. The psychometrics of PASTOR are discussed in section 7.3.4.

Upon completion of a PASTOR assessment, a three-page report is generated (see Section 6: Surveys, Questionnaires, and Other Data Collection Instruments – PASTOR) that summarizes all domains measured and displays them longitudinally once there are two or more assessments completed. Raw data will be stored in the PASTOR outcomes registry and made available to the research study after patient identifiers have been removed. It is planned that PASTOR will eventually include other validated measures relevant to pain, including the Patient Activation Measure, Pain Catastrophizing Scale, Tampa Scale for Kinesiophobia, Pain Self-efficacy Questionnaire and Chronic Pain Acceptance Questionnaire. Until these measures are added to electronic PASTOR assessment tool, these additional questionnaires will be administered in paper form at the same intervals that PASTOR is administered.

In February 2016, the Army Functional Restoration Workgroup determined that the Rolland-Morris Disability Score and the Canadian Occupational Performance Measure should be among the standardized outcome measures used by all Army FR programs, so these outcome measures are also included.

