11.0 Statistical/Data Analysis Plan

11.1 Statistical Considerations:

List the statistical methods to be used to address the primary and secondary objectives, specific aims, and/or research hypotheses. Explain how missing data and outliers will be handled in the analysis. The analysis plan should be consistent with the study objectives. Include any sub-group analyses (e.g., gender or age group). Specify statistical methods and variables for each analysis. Describe how confounding variables will be controlled in the data analysis

The statistical methods that will be used for each study aim are explained in section 11.3.

Approach to Missing Data.

The amount of missing data will be first quantified where possible, and determined by the amount of missing data that occurs, three indirect tests of the mechanism of missingness will be explored: (1) baseline demographic characteristics of those who ever and never missed data by group allocation will be compared (an indirect test to rule out missing completely at random [MCAR]); (2) the difference between mean utility scores of participants with missing and non-missing data will also be compared (an additional indirect test to rule out MCAR) and (3) controlling for the probability of providing missing data, the mean scores of those that never and ever missed in intervention and control groups will be compared (an indirect test of missing not at random [MNAR]). While analysis using mixed models allows all observed data to be included in the analysis under the assumption that the data are MCAR, if substantial missing data occurs, multiple imputation or mean conditional imputation will be used with subsequent sensitivity analyses to explore the impact of imputation on results. To address the issue of artificially reduced estimates of stochastic uncertainty produced by imputation, bootstrapping procedures will be used on the entire imputation and estimation process.

11.2 Sample Size Estimation:

Estimated required sample size: 152
Estimated participant drop out + withdrawal: 28%
Total enrollment requirement: 210
Total MAMC enrollment: 210

11.3 Data Analysis Plan:

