We will initially complete analyses without the inclusion of pre-randomization covariate information. In all analyses, the data will be examined for appropriateness of the statistical assumptions underlying fitted models (e.g., distribution of regression residuals, identification of multivariate outliers representing influential data points, tests for departures from linearity). The primary analysis will examine differences between the control and intervention groups' outcome scores at the 3 month assessment point. To control for inflation of Type I error rates due to co-primary outcomes, alpha will be set to 0.025 for each test of the outcome variables.

If recruitment targets are exceeded to a sufficient magnitude, secondary analyses of change in pain severity and physical function using responder analysis will also be performed. When consensus on minimally important difference (MID) exists, that MID will be used to define response. For PROMIS measures that do not have consensus MID measures, an improvement of one-half of one standard deviation on the PROMIS scale will be considered the minimally important difference for a positive response. Responder analyses require higher sample sizes to detect statistically significant differences but are the preferred method of assessing treatment effect, and permit meaningful comparisons between randomized clinical trials.⁷⁸

Aim 2: Identify prognostic factors that predict successful outcomes on pain severity and function following intensive interdisciplinary functional restoration.

In addition to IM vs standard care, secondary predictors of outcomes following FR will include baseline measures of: demographic variables (age, military rank, race, military occupation), pain characteristics (location, duration, character), psychosocial factors (depression, anxiety, anger); sleep quality and fatigue; medical board status for disability; duration of pain-related disability; prescription opioid dosage; and functional capacity tests for endurance and strength.

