Analytical Technique: We will use a multiple linear regression approach to determine the roles of patient activation, pain catastrophizing, self-efficacy, and pain acceptance with regard to the intervention outcomes. Baron and Kenny⁸⁶ described mediation and moderation testing and their work has been developed further by methodologists. We will use Hayes' conditional process tools⁸⁷ to test if patient activation, pain catastrophizing, self-efficacy, and pain acceptance are affected by the intervention and help explain the outcomes, that is, if they are a mechanism for how the intervention helps people (mediation). We will compare models with and without the mediating variables and partition the total effect of the intervention into indirect effects due to impact on hypothesized mediators and the remaining direct effects. Using interaction terms, we will also examine if these variables may moderate the relationship of the intervention on the outcomes, helping explain who is responding best to the intervention. This approach can be extended to determine if how the intervention works differs by participant characteristics, that is moderated mediation.

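### Aim 7 reads the indirect effect as the mechanism of IM but names no baseline mediator score, no baseline outcome score and no check for mediator-outcome confounding

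*Combined protocol and SAP*

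**What the plan says.** Aim 7 in section 11.3 asks whether patient activation, catastrophizing, self-efficacy or pain acceptance moderates or mediates the pain and function outcomes. The method opens: "We will use a multiple linear regression approach to determine the roles of patient activation, pain catastrophizing, self-efficacy, and pain acceptance". Conditional process tools then test whether IM changes these factors and whether they explain the outcomes, that is, "if they are a mechanism for how the intervention helps people (mediation". The decomposition follows: "We will compare models with and without the mediating variables and partition the total effect of the intervention into indirect effects", with the remainder taken as the direct effect.

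The text gives no equation, no covariate list, no form for the outcome (follow-up or change) and no sensitivity analysis. Aim 7 in section 9.4 adds nothing on these points. The template for section 11.1 asks how confounding will be controlled; the answer refers to 11.3 and then covers missing data. Aim 2, by contrast, states adjustment for baseline values of the co-primary outcomes and for treatment group.

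The baseline scores are scheduled. Section 10.1 places the first assessment before randomisation and says of the mediator questionnaires: "these additional questionnaires will be administered in paper form at the same intervals that PASTOR is administered".

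**The concern.** Randomisation protects the effect of IM on the mediator and the effect of IM on the outcome. It does not protect the path from mediator to outcome, because no patient is allocated to a level of catastrophizing or self-efficacy. A patient who starts high on catastrophizing and on pain will tend to stay high on both, so the two follow-up scores correlate within each arm even if neither influences the other. A regression of outcome on arm and mediator reads that correlation as the mediator's effect and multiplies it by whatever IM did to the mediator.

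The protocol's own account of the instruments makes this plausible. Section 10.2 describes catastrophizing scores as strongly correlated with perceived pain, and gives a test-retest correlation of 0.73 for self-efficacy. At stake is a published mechanism for IM that reflects stable differences between patients.

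**Working it through.** **Inputs from the plan.** Section 11.2 gives "Estimated required sample size: 152", "Estimated participant drop out + withdrawal: 28"% and "Total enrollment requirement: 210". These agree: 152 / (1 − 0.28) = 211.1, close to 210, and 1 − 152/210 = 27.6%. The check uses 152 analysed patients, 76 per arm; 1:1 allocation is assumed because the ratio is not stated. No power or sample size is given for mediation. Aim 1 says "alpha will be set to 0.025 for each test of the outcome variables"; Aim 7 states no level. The simulations used 4,000 or 3,000 trials per setting and counted false mediation when both paths were significant. A separate run used 2,000 trials and a 95% interval for the product of the paths.

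**Assumed inputs.** The documents give no trial values for these, so they are ranges: baseline mediator-outcome correlation r0 = 0.3 to 0.6; stability s (correlation of each follow-up score with its own baseline) = 0.6; IM shift in the mediator a = 0.3 to 0.5 SD. The true mediator effect is zero.

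**Data model.** With T the arm indicator and standardised scores:
- M1 = s·M0 + a·T + √(1 − s²)·e1
- Y1 = s·Y0 + c·T + √(1 − s²)·e2, with no M1 term
- corr(M0, Y0) = r0

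**Arm and mediator only.** Within arm, Var(M1) = 1 and Cov(M1, Y1) = s²·r0. The estimated mediator path is therefore b = s²·r0 instead of 0, and the spurious indirect effect is a·s²·r0. With s = 0.6, s² = 0.36:

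| r0 | b | indirect, a = 0.3 | indirect, a = 0.5 | false mediation, a = 0.3 | false mediation, a = 0.5 |
|---|---|---|---|---|---|
| 0.3 | 0.108 | 0.032 | 0.054 | 12% | 23% |
| 0.5 | 0.180 | 0.054 | 0.090 | 27% | 51% |
| 0.6 | 0.216 | 0.065 | 0.108 | 34% | 66% |

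The simulated indirect effects match the formula to within 0.001. A repeat simulation put the lower end at 10%. The product-interval run, with s = 0.5 and 0.7 and r0 = 0.3 and 0.5, gave 6% to 35% at a = 0.3 and 14% to 73% at a = 0.5.

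**Change scores for mediator and outcome.** Var(M1 − M0) = (1 − s)² + (1 − s²) = 2(1 − s), and the covariance of the two changes is (1 − s)²·r0. So b = (1 − s)·r0/2 = 0.2·r0. The indirect effect runs from 0.3 × 0.06 = 0.018 to 0.5 × 0.12 = 0.060 SD, with false mediation in about 5% to 29% of trials. The bias is smaller but not removed.

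**Boundaries.** At r0 = 0.5 and s = 0.6, false mediation is 14% for a shift of 0.2 SD and 6% for 0.1 SD. In the product-interval run, with no shift the indirect effect averages zero and the rate is at most 4.4%; with r0 = 0 it is at most 3.8%.

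**Both baseline scores in both equations.** What remains is the correlation of e1 and e2. If that is zero, b = 0 and the rate is 3% to 5%. If a common cause after baseline gives e1 and e2 a correlation ρ, then b = ρ even after adjustment. At a = 0.5, r0 = 0.5, s = 0.6:

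| ρ | adjusted indirect effect (0.5 × ρ) | false mediation |
|---|---|---|
| 0.1 | 0.05 | 21% |
| 0.2 | 0.10 | 66% to 69% |
| 0.4 | 0.20 | 96% to 98% |

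The ranges in the last column come from separate runs.

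**The case against.** A reader might infer that the plan excludes baseline scores. It does not: Aim 7 is silent, and linear regression and the named tools accept covariates. That limits the claim to an omission. The omission still matters, because Aim 2 states baseline adjustment and Aim 7 does not, so an analyst following Aim 7 as written has no instruction to adjust.

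A reader might also infer that IM will appear to work through these factors whatever happens. The bias needs IM to move the mediator. Standard care already includes cognitive behavioural group therapy (section 10.1, Table 2), so the extra shift from IM could be small, and the false-positive rate then falls towards its nominal level. This objection stands as a condition on the size. It does not remove the problem, since a visible shift is the situation in which mediation would be claimed.

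A third inference is that two covariates solve the problem. The 3% to 5% figure depends on routing all confounding through baseline. All patients go through functional restoration after the pre-FR stage, so shared causes after baseline are plausible.

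Finally, it would be too strong to say that every patient has all the baseline scores. Section 10.2 records approval for the patient activation measure as pending, the moderate-flexibility window in Aim 6 accepts a baseline up to two days after treatment start, and section 11.1 plans for missing data. The scores are scheduled, which is enough for the fix but means that gaps must be handled.

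**Conclusion.** The point holds as an omission in a secondary aim. Aim 7 gives the indirect effect a causal reading without naming the baseline scores or any check that this reading needs. If IM shifts a mediator that shares stable causes with the outcome, the arm-and-mediator model produces a spurious indirect effect of about 0.03 to 0.11 SD and false mediation in about 10% to 66% of trials; change scores give about 5% to 29%. These sizes rest on the assumed correlations, stability and IM shift, none of which the documents supply, and they fade as the shift approaches zero. Baseline adjustment is needed but not sufficient: at a 0.5 SD shift and baseline correlation 0.5, residual correlations of 0.1 to 0.4 leave about 21% to 98%.

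A reader might extend this to the trial's main result. The documents do not support that: the primary analysis in section 11.3 compares the randomised arms at 3 months and contains no mediator. The change should be made before Aim 7 is analysed.

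**What to change.** In section 11.3, Aim 7, add: *The mediator equation and the outcome equation each include the baseline value of that mediator and the baseline value of that outcome. Missing baseline values are handled by the imputation plan in section 11.1.*

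Add a sensitivity analysis that reports the indirect effect over a range of residual correlations between the mediator and outcome equations (0.1 to 0.4 would cover the values examined here), and state the correlation at which the effect would vanish. Report the indirect effect as conditional on no residual mediator-outcome confounding.

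The cost is small. No new data collection is needed; the work is SAP wording, one added analysis and the handling of missing baseline questionnaires, including patient activation if that measure was not approved.

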12.0 Participant Information

12.1 Subject Population:

Active duty service members with chronic pain

12.2 Age Range:

- 0-17
- 18-24
- 25-34
- 35-44
- 45-54
- 55-64
- 65-74
- 75+

12.3 Gender:

- Male
- Female

12.4 Special categories:

- Minors /Children - "You must also consider the requirements of 45 CFR 46 Subpart D and DoDI 3216.02, Enclosure 3, paragraph 7.d."
- Students
- Employees - Civilian - "You must also consider the requirements of DoDI 3216.02, paragraph 7.e."
- Employees - Contractor
- Resident/trainee
- Cadets /Midshipmen - "You must also consider the requirements of DoDI 3216.02, Enclosure 3, paragraphs 7.e. and 12."
- Active Duty Military Personnel - "You must also consider the requirements of DoDI 3216.02, Enclosure 3, paragraph 7.e."
- Wounded Warriors - "Depending on your intended subjects' status, you may also need to consider the requirements of DoDI 3216.02, Enclosure 3, paragraph 7.e."
- Economically Disadvantaged Persons - "You must also consider the requirements of 32 CFR 219.111 (b)."
- Educationally Disadvantaged Persons - "You must also consider the requirements of 32 CFR 219.111 (b)."
- Physically Challenged (Physical challenges include visual and/or auditory impairment)
- Persons with Impaired Decisional Capacity - "You must also consider the requirements of 10 USC 980."
- Prisoners - "You must also consider the requirements of 45 CFR 46 Subpart C and DoDI 3216.02, Enclosure 3, paragraphs 7.b. and 7.c."
- Pregnant Women, Fetuses, and Neonates
- Non-English Speakers
- International Research involving Foreign Nationals - Headquarters Review is necessary

12.5 Inclusion Criteria:

Order Number	Criteria
1	Significant functional impairment due to pain, requiring modification of military duties.
2	Physically able to participate in up to four hours of physical activity (strength, flexibility, endurance training) per day: 
 1. Can stand up from and sit down on floor independently 2. Can complete at least 6 minutes of Naughton Treadmill Protocol. . 3. Able to complete at least 2 of the following: 
 -Lift 20 lbs from floor to knuckle height. -Lift 20 lbs from floor to shoulder height. -Carry 20 lbs at least 40 feet.
3	Inadequate response to previous less intensive treatment
4	Expresses motivation to take active role in regaining function

12.6 Exclusion Criteria:

Order Number	Criteria
1	Major surgeries within past 6 months or planned within next 6 months.
2	Unstable psychological disorders

3	Active substance use disorder
4	High dose opioids of ≥90 milligrams of morphine equivalent doses (MED)/day
5	In the Medical Evaluation Board process and without defined availability for any treatment scheduling

13.0 Recruitment and Consent

13.1 Identification and Selection of Subjects:

Subjects will be selected from among the patients referred to the IPMC for whom an IPMC physician recommends participation in FR and who are determined by an IPMC physical therapist to meet minimal standards of physical function required for successfully FR participation.

13.2 Recruitment Process:

Study participants will be recruited from the population of patients who are referred to the Madigan Interdisciplinary Pain Management Center and who are determined by the treating physician to be a candidate for the FR program. If the patient is willing to commit to this intensive treatment approach, he/she will be evaluated by a physical therapist to determine if he/she has the physical stamina to successfully participate in FR. If so, his/her commanding officer will be contacted by a nurse case manager and asked to approve the patient's absence from work as needed for the six-week program. Any patients who receive approval from their commanding officer to participate in FR will be considered for inclusion in the study.

13.3 Compensation for Participation:

No compensation for study

13.4 Eligibility Assessment Process:

A partial HIPAA waiver of authorization will be requested to allow the research coordinator or research assistant to perform a prescreen of medical records of potential subjects to determine if they have any excluding conditions.

13.5 Consent Process:

Are you requesting a waiver or alteration of informed consent?

Yes No

What type?

Waiver of documentation of informed consent
 Waiver or alteration of informed consent

Please explain why you qualify for a waiver or alteration of informed consent:

Waiver is requested to determine if subjects are eligible for participation. Eligible patients interested in participation will undergo informed consent.

Please explain the consent process:

Following the prescreen process, any potential subjects will meet with the research coordinator or research assistant who will explain the study and request that the patient participate. Patients who express an interest in participating will be consented. Patients who decline to participate in the study will be given the option of proceeding with the integrative modalities program and/or the functional restoration program as recommended by their physician.

Research staff will approach eligible patients during an out-patient IPMC visit or by telephone, explain the study and answer questions about the study (refer to Enrollment Script). If the patient express willingness to participate in the study at the time of this discussion, they will be consented. If eligible patients do not decline participation but request more time to consider participation, the research staff will re-contact them within 1 week of the initial contact to enable them to consent or decline. Eligible patients who decline study participation will be asked to share reasons for refusal. A confidential list of patients who have been approached but who are not enrolled in the study will be maintained by the research staff to ensure that no patient is approached more than once. A HIPAA waiver of authorization is requested for the creation and maintenance of this list, as it poses minimal risk to patient privacy and is essential to ensure that patients do not perceive coercion to participate in the study. The number of eligible patients, those approached, enrolled, and the reasons for refusal, will be recorded.

13.6 DoDI 3216.02 requires an ombudsman to be present during recruitment briefings when research involves greater than minimal risk and recruitment of Service members occurs in a group setting. If applicable, you may nominate an individual to serve as the ombudsman.

- N/A
- Propose ombudsman

13.7 Withdrawal from Study Participation:

Explain the process for withdrawal and specify whether or not the subjects will be given the opportunity to withdraw their data their data/specimens in the event they wish to withdraw from the study

Participants may elect to discontinue participation in the study at any time. This decision will not affect their eligibility to continue the integrative modalities program or functional restoration program. If they elect to discontinue participation in the integrative modalities (IM) and/or functional restoration (FR) program, they will be offered other appropriate therapies offered in the IPMC, such as medication management and/or interventional pain therapies. On rare occasions patients in the IM program or FR program are disenrolled from the program by the clinical team. Reasons include repetitive missed appointments and/or behavior that is disruptive to the treatment group. Patients demonstrating these behaviors are counseled and given the opportunity to engage more effectively in treatment prior to disenrollment.

